Helmet CPAP for Infants and Pediatric Patients with Acute Respiratory Distress

NCT04764929

Principal Investigator: [name]

August 23, 2021

Background

Study Purpose and Rationale:

Continuous positive airway pressure (CPAP) has become standard of care in pediatric patients with acute lung infections such as bronchiolitis and pneumonia. CPAP is currently delivered with several different patient interfaces: facemask, nasal mask and nasal prongs. In order for CPAP to be most effective there should be very little leak between the patient and the interface. This can be challenging in young pediatric patients as they are often not as compliant as adults with maintaining their interfaces in place. Leaks with the use of traditional CPAP interfaces may decrease effective delivered pressures also increase the risk of aerosolization of viral particles. Thus, an ideal interface would be one that forms a complete seal and is well tolerated. The use of a helmet interface to deliver CPAP could offer an effective alternative to traditional nasal or facemask CPAP interfaces and more consistently provide the prescribed pressure and decrease the chance of aerosolizing viral particles. Thus, we propose a pilot study to determine tolerability of helmet CPAP in children one month to five years of age with acute respiratory distress admitted to the pediatric ICU (PICU). A prior randomized controlled trial in the United States demonstrated helmet CPAP significantly decreases the intubation rate (18.2% versus 61.5%) compared to face mask CPAP in 83 adults with acute respiratory distress syndrome (ARDS).¹ The rate of adverse events were similar with three interface-related skin ulcers in each group: 6.8% in the helmet group had neck ulcers and 7.6% in the face mask group had nose ulcers. By achieving a complete seal with the use of a helmet CPAP, constant pressures can be delivered to the patient compared to air leaks often seen with traditional interfaces such as a full facemask or nasal mask. In a multicenter randomized controlled trial in Italy, 30 infants (children under one year of age) with respiratory syncytial virus (RSV) acute respiratory failure were randomized to receive CPAP by helmet (n = 17) or facial mask (n = 13).² Helmet CPAP had a lower treatment failure rate due to intolerance (17% vs 54%, P = .009) and fewer infants required sedation (35% vs 100%, P = .023). There was no difference in the rate of invasive mechanical ventilation and no major adverse events were observed. Another pediatric study in Spain enrolled infants less than three months of age admitted to the PICU with bronchiolitis.³ Sixteen patients were randomized to receive CPAP via a helmet or nasal prongs for the first hour then crossed over to the other group for another hour (helmet then nasal prongs or nasal prongs then helmet). Modified Wood's Clinical Asthma Score (M-WCAS) was measured at 30 minute intervals and failure was defined as the need for further respiratory support. CPAP significantly reduced respiratory distress in both groups and the failure rate was similar in both groups demonstrating CPAP delivered by nasal prongs and CPAP delivered by helmet are similar in terms of efficacy in young infants with acute bronchiolitis. Prior clinical trials have demonstrated efficacy in adults with acute respiratory distress syndrome, superior tolerance and improved respiratory scores compared to nasal/facial CPAP in infants, and no major safety concerns were identified with the use of helmet CPAP. We propose a prospective pilot study to (1) determine if infants and pediatric patients requiring CPAP in the PICU will tolerate helmet CPAP for at least four hours and (2) measure changes in the respiratory rate, oxygen saturation, heart rate and blood pressure over four hours. If helmet CPAP is found to be well tolerated in this small cohort, we will move forward with a larger study.

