
Study Design:

Prospective, non-randomized, single arm, interventional study.

Inclusion Criteria:

23AUGUST2021

1 month to 5 years of age (inclusive) admitted to the PICU with community acquired pneumonia or bronchiolitis, having been stable on nasal or facemask CPAP for at least two hours, and parental informed consent.

Exclusion Criteria:

Age less than 1 month or greater than 5 years, positive for COVID19, need for invasive mechanical ventilation or higher levels of non-invasive ventilation such as bi-level positive airway pressure (BPAP), unresponsiveness (GCS 8 or less), hypotension as defined as a systolic blood pressure less than 5th percentile for age, existing head or neck trauma, known or suspected air leak syndrome (pneumothorax, pneumomediastinum, sub-cutaneous emphysema), known or suspected increased cranial pressure, non-English speaking parent.

Methods:

Convenience sampling will be used to enroll 30 patients admitted to the Pediatric Intensive Care Unit (PICU) already receiving CPAP through a facemask or nasal prongs or mask for at least two hours. All patients will be transitioned to the Vyatil nonpowered oxygen tent system (Rochester, NY) by trained respiratory therapists per the manufacturer's instructions: patient's neck circumference will be measured with a soft tape measure to ensure appropriate sizing. The helmet will be connected to at least 30 liters per minute of high flow medical air with an oxygen blender. The expiratory limb will be attached to the PEEP valve (initially set at 5 centimeters of water pressure) connected to a HEPA filter to prevent any viral particles from being released into the environment. A disposable manometer will be used to measure the pressure within the helmet. Once the flow to the helmet interface is on, the helmet will be sealed and secured with the system's arm straps.

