Vital signs will be recorded hourly per standard PICU care (respiratory rate, pulse oximetry, pulse, blood pressure) along with transcutaneous carbon dioxide (CO₂). The presence of adverse events (aspiration pneumonia, skin breakdown, hypotension, eye irritation, gastric distension, other) will be recorded prospectively along with total time on helmet CPAP, reason for discontinuation (patient improved, escalation of respiratory support/death, or patient not tolerating), and clinical outcome (discharged home, transferred out of PICU, intubated or death). Laboratory data (Respiratory viral panel, blood gas, complete blood count, C-reactive protein) and chest radiograph results will be recorded if obtained by the treating healthcare provider.

Primary Outcome Measure: Percentage of patients that tolerate helmet CPAP for at least four hours. Tolerance is defined as the successful application and maintenance of helmet CPAP without any unplanned, prolonged (>5 minutes) removals or disruptions. We hypothesize that at least 80% of the patients will tolerate the helmet CPAP interface for four hours.

Secondary Measures: Change in vital signs (respiratory rate, oxygen saturation, heart rate, and systolic blood pressure) over four hours. We hypothesize that vital signs will improve or remain stable throughout the application of helmet CPAP as compared to pre-helmet CPAP.

Statistical Plans:

We will present median values of vital signs longitudinally, median duration of helmet CPAP in hours, and reasons for discontinuation along with clinical outcomes and laboratory testing and imaging if available.

Study Procedures:

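### The secondary outcome is change from pre-helmet CPAP, but the stated analysis reports group medians of the levels and ignores the pairing within each child

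*Protocol*

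**What the plan says.** Study Purpose and Rationale gives the second aim as to "measure changes in the respiratory rate, oxygen saturation, heart rate and blood pressure over four hours". Secondary Measures defines the outcome as "Change in vital signs (respiratory rate, oxygen saturation, heart rate, and systolic blood pressure) over four hours" and adds the hypothesis: "We hypothesize that vital signs will improve or remain stable throughout the application of helmet CPAP as compared to pre-helmet CPAP".

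Study Design describes a "Prospective, non-randomized, single arm, interventional study". Under Methods, "Convenience sampling will be used to enroll 30 patients". Eligible children are aged from 1 month to 5 years and enter "having been stable on nasal or facemask CPAP for at least two hours". Vital signs are recorded hourly, and total time on helmet is recorded.

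Statistical Plans has one sentence. Its only provision for vital signs is "We will present median values of vital signs longitudinally". The protocol mentions no change from baseline, within-child summary or interval, and does not say which pre-helmet reading is the reference.

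**The concern.** The outcome and hypothesis are about change; the stated analysis is about levels. With one arm, the only comparator is the same children before the switch. The data are therefore paired by design, although the protocol does not use that word. A table of hourly medians discards the pairing.

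Two consequences follow. First, the difference between two medians can differ from the median of the differences, even in sign. Second, normal vital signs differ widely between a one-month-old and a five-year-old. That spread enters the difference of medians but cancels in a within-child change. What is at stake is how clearly a cohort of 30 answers the protocol's own question about vital signs, not the validity of the primary result.

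**Working it through.** **Inputs from the protocol.** n = 30; one arm; hourly readings; hypothesised tolerance of at least 80%, so 0.80 × 30 = 24 children on helmet at hour 4 serves as an illustration. The protocol states no SD, correlation or effect size for any vital sign, so there is no figure of its own to reproduce.

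**Assumptions.** Respiratory rate in breaths/min, normally distributed; between-child SD *s* = 8, 12 or 15; SD of within-child change *d* = 4, 6, 8 or 12; complete data; 100,000 simulated cohorts per cell.

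**1. The two summaries are different quantities.** Rates of 30, 40, 50 becoming 41, 51, 29 have medians 40 and 41, a difference of +1. The changes are +11, +11, −21, with median +11. The sign can also reverse: 30, 40, 50, 60, 70 becoming 28, 38, 52, 58, 68 gives a difference of medians of +2 and a median change of −2.

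**2. Precision by formula.** For bivariate normal readings with equal SD *s* and correlation ρ, in large samples:

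- Var(difference of medians) = (2*s*²/n)(π/2 − arcsin ρ)
- Var(median change) = (π/2) · 2*s*²(1 − ρ)/n
- Ratio = (π/2 − arcsin ρ) / [(π/2)(1 − ρ)]

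At ρ = 0.7: (1.571 − 0.775)/(1.571 × 0.3) = 0.795/0.471 = 1.69. At ρ = 0 the ratio is 1.00, and at ρ = −0.3 it is 0.92. The gain therefore needs positive within-child correlation.

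**3. Simulation at n = 30, equal variances.** Here ρ = 1 − *d*²/(2*s*²). For *s* = 12 and *d* = 4, 6, 8, 12, ρ is 0.94, 0.88, 0.78, 0.50 and the ratio is 3.2, 2.3, 1.8, 1.3. The least favourable cell (*s* = 8, *d* = 12, ρ about −0.12) gives 0.96, slightly against the paired summary. The ratio has no units, so it carries over to heart rate and systolic pressure if these are roughly normal. It does not carry over to oxygen saturation, which is bounded.

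**4. Simulation at n = 30, change added independently to baseline.** Variance ratios:

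| *s* | *d* = 4 | *d* = 6 | *d* = 8 | *d* = 12 |
|---|---|---|---|---|
| 8 | 2.41 | 1.81 | 1.52 | 1.26 |
| 12 | 3.27 | 2.40 | 1.98 | 1.52 |
| 15 | 3.83 | 2.84 | 2.30 | 1.75 |

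At *s* = 12 the SEs (difference of medians vs median change) are 1.6 vs 0.9, 2.1 vs 1.3, 2.5 vs 1.8 and 3.3 vs 2.7. Over the grid, the two summaries differ by 2 breaths/min or more in 11.5% to 49.8% of cohorts. With a true mean fall of 3, the difference of medians shows a rise in 1.6% to 19.6% of cohorts, and the median change in under 0.1% to 13.3%.

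**5. Illustration with 24 children, both summaries on the same 24.** The ratio is 1.27 to 3.55, and they differ by 2 or more in 14.7% to 53.4% of cohorts.

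**6. A distribution-free interval is available.** Order statistics with Binomial(n, 0.5) give 1 − 2·P(B ≤ 9) = 95.7% for the 10th to 21st ordered change of 30. For 24 children, 1 − 2·P(B ≤ 6) = 97.7% for the 7th to 18th; the 8th to 17th would give only 93.6%.

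**The case against.** The strongest reply is that this is close to a preference. The protocol plans only to present medians. It states no test, interval or threshold for vital signs, so a smaller SE changes no planned inference, and progression to a larger study depends on tolerability. Medians shown from before the switch to hour 4 do display the cohort's course, and an SAP that is not shown may add change scores. All of this bears on importance, and it is why the point is not rated higher. It does not remove the mismatch: the protocol chose a summary, and that summary is not of the outcome it defines.

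A second reply is that the size rests entirely on assumed SDs and that the extremes come from different cells. That is fair. The ratio of 3.8 belongs to *s* = 15, *d* = 4, where the summaries differ by 2 or more in about 22% of cohorts. The 50% belongs to *s* = 15, *d* = 12, where the ratio is about 1.75. Where the difference of medians points the wrong way in about 20% of cohorts, the median change does so in about 13%. The 2 and 3 breaths/min benchmarks are illustrative, and the three-child example is contrived to show possibility, not likelihood.

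A third reply is that an on-helmet summary describes only children still on helmet. That stands as a limitation. However, the hypothesis concerns the period of helmet application, so this is the summary that matches it, provided the counts are shown.

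**Conclusion.** The concern holds. The outcome is change from the pre-helmet value, while the stated analysis summarises levels and ignores the pairing. The stated summary is not invalid: under a common shift with symmetric scatter it has the same target. It is usually less precise, with 1.3 to 3.8 times the variance under the additive model at n = 30, about equal when a child's two readings are uncorrelated, and marginally better if the correlation is negative. Positive correlation is plausible in this age range but is not given in the protocol. The figures assume normal data and SDs chosen for illustration, and they do not cover oxygen saturation. This is an improvement that should be made because it costs almost nothing; no decision in the protocol rests on it.

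**What to change.** In Statistical Plans:

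- Name as baseline the last value recorded on nasal or facemask CPAP before the switch.
- Keep the longitudinal medians and add, for each vital sign, the median within-child change from baseline at hours 1 to 4 with a 95% CI.
- Make the on-helmet summary the main one and give the number of children on helmet at each hour.
- As a supplement, show all children through hour 4, noting that those values mix in later treatment.

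The cost is about two sentences. No new data are needed: vital signs are recorded hourly, time on helmet is recorded, and every child has at least two hours of CPAP before the switch. The order-statistic interval needs no model. The one drawback, that the main summary covers only children still on helmet, is made visible by the hourly counts and the supplement.
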